**Table 2: Changes in Costs among Aetna Patients Randomized to CM or EC: National Data**

	Care Management (mean \$±SD)			Educational Control (mean \$±SD)		
	6 Mos Pre	6 Mos Post	Difference	6 Mos Pre	6 Mos Post	Difference
Aetna BH \$/member	5,210±8,370	934±2,210	-4,277±7,926	6,048±6,347	3,492±7,621	-2,556±8,461

**C.4. NNDC Multisite mood CCM implemented by existing providers improves outcomes.** In a randomized controlled pilot study we determined the effectiveness of a cross-diagnosis mood CCM compared to education control in a cohort of outpatients with unipolar depression or bipolar disorder from four sites affiliated with the National Network of Depression Centers (NNDC). NNDC is the nation's largest network of academic and community-affiliated mental health and primary care clinics representing a diverse practice size and patient population. Existing care managers at four NNDC sites (Ann Arbor, Palo Alto, San Francisco, Denver) were trained by study investigators to implement the CCM using Enhanced REP. Sixty patients (mean age=46, 40% bipolar diagnosis, 73% female, 17% African-American) with mood disorders were identified using chart reviews and randomized to CCM or usual care. CCM included phone-based self-management and care management as well as guideline dissemination to providers. Repeated measures analyses comparing changes in 3 and 6-month outcomes revealed clinically significant probability of depression remission (>50% PHQ-9 score reduction and <=9 on PHQ-9 in 6 months): 50.1% for CCM vs. 19.0% for EC group (OR=9.4, p=.04) and improved well-being (positive symptoms based on the Internal State Scale-ISS - Cohen's D=.36).

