**Table 3: 6-Month Outcomes Comparing CCM vs Education Control (EC): Repeated Measures Analysis**

Outcomes(N=60)	CCM (N=29)			EC (N=31)			Repeated measures results		
	Baseline	3-mon	6-mon	Baseline	3-mon	6-mon	Beta	T(p)	Effect(D)
PHQ-9	13.7 (7.5)	9.3 (6.5)	6.3 (4.2)	16.8 (6.5)	14.0 (6.6)	11.9 (6.8)	-1.24	-1.37(.17)	-.22
50% drop: PHQ-9 and PHQ-9 <=9			50.0%			19.0%	OR=9.4; Chi-sq= 4.18; p=.04		
ISS-Wellbeing	13.0 (7.9)	15.8 (8.3)	20.4 (7.8)	10.2 (6.9)	12.5 (7.8)	12.4 (8.1)	2.22	2.35(.02)	.36

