**Figure 2: Implementation of Mood CCM across Health Plan, Practices, and Patients**

clinician who treats their mood disorder (i.e., prescribes psychotropic medications). Comorbidities will be ascertained from Aetna eTUMS chart reviews conducted by the RAs.

program evaluation, and will be blinded to randomization assignment. (S)he will be trained by Aetna on their well-established call implementation program across time zones (**Section C.5.c**) and by study investigators in human subjects risk reduction procedures used in prior studies (8, 50) that will minimize risk while not compromising study internal validity (8). The initial assessment (described below) will include a brief survey baseline factors, including demographics, employment, whether they were the Aetna enrollee or a family member, and primary

**C.5.c. Existing Aetna Infrastructure Used in this Study.** The following components are of specific relevance:

1. The registry/database consists of four main components and will be used to identify potentially eligible patients as well as ascertain utilization and other outcomes data (see variable descriptions below). The Electronic Total Utilization Management System (**eTUMS**), a proprietary care management tool is populated by

claims data augmented by customizable care manager input; major claims events, such as hospitalization, result in automatic care manager notification. The **pharmacy claims database** accrues prescription claims daily, including drug and dose, and is downloaded to eTUMS on a weekly basis. **Laboratory claims data** are similarly downloaded on a monthly basis; laboratory reports contain the name of the test, while reports from larger laboratories also provide results. Thus these registries will provide the data necessary to measure guideline-concordant care (e.g., non-filling of mood disorder prescriptions, non-completion of cardiometabolic laboratory tests). The fourth component, **Aetna claims data**, includes use and cost data for Aim 3.

**2. The Aetna care management infrastructure is substantial and stable.** The masters level Aetna care managers who participated in the pilot will serve as the CCM care managers. They have a minimum of 5 years of care management experience with Aetna, providing short-term or ongoing care management for an average of 300 beneficiaries per year across multiple time zones and patient schedules.

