- **Patient Clinical Assessment:** During the first 10 weeks, each fourth call (monthly) will also include an assessment of overall clinical and treatment status (~15 minutes). Assessment will include the 9-item Patient Health Questionnaire (PHQ-9)(102, 103) to assess depressive symptoms, the 8-item Internal State Scale (ISS; (52, 104-106) to assess manic symptoms and well-being; medication use, adherence (7, 107), and side effects. The intake contact includes identification of care providers and recent contacts, and each follow-up call will include a focus on maintaining engagement/continuity. These calls will continue on a monthly basis for up to one year of participation, with additional phone contacts made to follow up in the event of a hospitalization or emergency room visit based on our RCTs (50-53, 108).
- **Claims Database/Registry Review:** The care manager will also use the eTUMS registry to track inpatient hospitalizations, pharmacy and laboratory status. These data, available in a clinically useful time frame (Section C.5.c), will assist the patient with trouble-shooting illness management, and assist the care manager in identifying opportunities for intervention or quality enhancement.
- **Provider communication:** Care management strategies to date have under-emphasized provider engagement (9). In the mood disorders CCM, the care manager will contact the provider at the time of patient enrollment to introduce the CCM and to determine how best to integrate CCM procedures into the provider’s practice needs. This initial contact will identify the optimal mode of communication between

provider and care manager, as well as delineation by the provider for the care manager of the expected care plan going forward (frequency of visits, medications, lab tests such as cardiometabolic monitoring). After this initial engagement and care planning contact, the care manager will contact the provider in the event of hospitalization, emergency room visit, or development of a new clinical issue, as well as to cue them if there is a crisis encounter (e.g., suicidality).

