**CCM-3: Provider Decision Support:** As noted above, the care manager will have obtained clinical assessment data each month plus eTUMS-based data on pharmacy refills (weekly) and laboratory utilization (monthly). Using these multi-component assessment and treatment data, s/he will communicate situation-specific treatment options based on clinical practice guidelines for bipolar disorder (96, 98). For instance in the case of unipolar depression, non-response or partial response to medication (defined as <50% reduction in PHQ-9 score and PHQ-9  $\leq$ 9) would be followed by the care manager providing a series of treatment options based on current guidelines (97, 109). For those with bipolar disorder and presence of subtherapeutic lithium levels and manic symptoms, the care manager would also outline options based on clinical practice guidelines (110). It is important to note that, as in our prior studies (50-53, 108), the CCM is designed to supplement care and does not replace or control provider decision-making. That is: clinical decision-making remains in the hands of the provider. CCM therefore enhances care processes by: (a) enhancing patient skills to facilitate treatment participation, (b) offering the provider timely information, and (c) outlining situation-specific evidence-based treatment options.

**C.5.e. Implementation Procedures.** The study will be managed by the **Aetna Joint Operating Committee** led by Drs. [name] and Un and includes [name], PsyD, Aetna Clinical Specialty Programs Head, and [name], Aetna Head of Program Development (Section C.5.k, see support letter from [name]). We will implement the CCM using Enhanced REP (76, 77, 79). Our research implementation infrastructure will provide, keeping with the theme of “light footprint” of research, the customized **package** of CCM procedures (see Appendix), supported by 16 hours of **training** at study initiation, followed by ongoing **technical assistance**. CCM Fidelity monitoring will be incorporated into ongoing Aetna CM audits (Section C.5.c).

**Packaging** includes an implementation manual for all three CCM components developed by [name] as well as the secure web-based self-management program for care managers and patients for the CCM-1 component (52, 95).

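### The CCM-3 example for unipolar depression defines non-response with PHQ-9 ≤9, the remission side of the cut-off, so no patient scoring 10 or more meets it; confirm the sign in the source file and correct it

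*Combined protocol and SAP*

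**What the plan says.** In section C.5.d, under CCM-3, the protocol illustrates provider decision support in unipolar depression. The trigger is "non-response or partial response to medication (defined as <50% reduction in PHQ-9 score and PHQ-9", and the next characters in the text are a less-than-or-equal sign and 9. Meeting the trigger "would be followed by the care manager providing a series of treatment options based on current guidelines".

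The same cut-off appears in the pilot results. Section C.4 reports a "clinically significant probability of depression remission (>50% PHQ-9 score reduction and <=9 on PHQ-9 in 6 months", and the matching row of Table 3 is labelled "50% drop: PHQ-9 and PHQ-9 <=9". In both places ≤9 marks a good outcome.

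On delivery, the CCM-2 text in section C.5.d provides for PHQ-9 assessments at calls about which it says: "These calls will continue on a monthly basis for up to one year of participation". Section C.5.e says the package "includes an implementation manual for all three CCM components" and that "CCM Fidelity monitoring will be incorporated into ongoing Aetna CM audits".

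**The concern.** The example reverses the percentage half of the pilot's remission rule (from more than 50% to less than 50%) but leaves the absolute half as it was. Non-response is therefore defined as too small a reduction together with a score already at the remission level. Patients who stay at 10 or more, for whom treatment options matter most, cannot meet it. Patients at 9 or below with a modest drop can.

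CCM-3 is one of the three core elements of the intervention, and this is the only numeric PHQ-9 threshold that the protocol gives for prompting provider decision support. What is at stake is whether CCM-3 is delivered as intended to unipolar patients, and whether the fidelity audits check the right behaviour. A manual or audit tool that copied the printed rule would score the wrong action as correct.

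**Working it through.** **Inputs**

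- Printed trigger (C.5.d, CCM-3): reduction below 50% and PHQ-9 ≤9.
- Pilot remission measure (C.4, Table 3): reduction above 50% and PHQ-9 ≤9.
- Pilot mean scores (Table 3): EC 16.8, 14.0, 11.9; CCM 13.7, 9.3, 6.3.
- Assumption: PHQ-9 takes whole-number values from 0 to 27. The protocol does not state the range, and the result for the printed rule does not depend on the upper limit.

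**Formulas.** Let b be the reference score and f the current score.

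- Printed rule: (b − f)/b < 0.5 and f ≤ 9, which is b/2 < f ≤ 9. This requires b < 18.
- Sign-corrected rule: (b − f)/b < 0.5 and f > 9, which is f > b/2 and f ≥ 10.

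**Scores flagged, for reference scores of 10 or more**

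| Reference score b | Printed rule flags f = | Sign-corrected rule flags f = |
|---|---|---|
| 10–11 | 6–9 | 10 or more |
| 12–13 | 7–9 | 10 or more |
| 14–15 | 8–9 | 10 or more |
| 16–17 | 9 | 10 or more |
| 18–19 | none | 10 or more |
| 20–21 | none | 11 or more |
| 22–23 | none | 12 or more |
| 24–25 | none | 13 or more |
| 26–27 | none | 14 or more |

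There are 18 × 28 = 504 possible pairs with b from 10 to 27. The printed rule flags 2×4 + 2×3 + 2×2 + 2×1 = 20. The sign-corrected rule flags 10×18 + 2×17 + 2×16 + 2×15 + 2×14 = 304. No pair meets both, since one rule needs f ≤ 9 and the other f ≥ 10. These are counts of score combinations, not of patients.

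**Single cases**

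- 20 to 18: 10% reduction, f = 18. Printed: not flagged. Corrected: flagged.
- 14 to 9: 5/14 = 36% reduction, f = 9. Printed: flagged. Corrected: not flagged.

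**Reference score.** The protocol does not say whether the reduction is taken from the first study score or the previous monthly one.

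- Printed rule, 20 to 14 to 9, last step: 11/20 = 55% from the first score (not flagged), but 5/14 = 36% from the previous score (flagged).
- Corrected rule, 24 to 18 to 12, last step: 12/24 = 50% from the first (not flagged), but 6/18 = 33% from the previous (flagged).

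Under either reading, the printed rule flags no score of 10 or more.

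**Pilot means as example paths**

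- EC: (16.8 − 14.0)/16.8 = 17% and (16.8 − 11.9)/16.8 = 29%, both scores above 9. The printed rule flags neither visit; the corrected rule flags both.
- CCM: (13.7 − 9.3)/13.7 = 32% at 9.3, then (13.7 − 6.3)/13.7 = 54% at 6.3. The printed rule flags neither visit; the corrected rule flags only the first, by 0.3 points.

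Group means show which scores each rule reaches, not how many patients would be missed. EC patients do not receive CCM-3 at all.

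**The case against.** The strongest objection is that the point rests on one symbol. Comparable inequalities in sections C.3 and C.4 and in Table 3 came through as plain characters, whereas this one came through as a converted mathematical symbol and could have been misread. If the source has a greater-than-or-equal sign, the reversal disappears, leaving only a one-point question at a score of exactly 9. This stands as a limit, and it is why the first step is to check the source file. It does not show that the sign was misread.

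Second, the rule is introduced as an example. The sentence before it gives care managers a general duty to pass on options using all the assessment and treatment data, so a patient at 20 is not formally excluded. That is correct. Still, the wording is that of a definition, and no other numeric PHQ-9 threshold for this action is given.

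Third, much would limit the effect in practice. Of the care managers, section C.5.c says "They have a minimum of 5 years of care management experience with Aetna". The same section provides for medical oversight, audits three times a month and a suicide-risk protocol. Table 4 has assessment data sent to the provider, CCM-2 adds other provider contacts, and section C.5.e adds training and weekly calls. Treatment decisions stay with the provider. These safeguards reduce the likely harm but do not correct the text, and because fidelity is checked through the audits, they could carry the error.

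Finally, the implementation manual is not part of the text reviewed, so whether it repeats the rule is unknown.

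**Conclusion.** The concern holds. The printed example contradicts the purpose of the trigger and the document's own use of ≤9 as part of remission. From a first score of 10 or more it reaches only 20 of 504 score combinations, all at 9 or below, and it has nothing in common with the sign-corrected rule.

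The conclusion assumes that the sign was read correctly from the PDF; confidence is medium for that reason. The effect is confined to delivery and fidelity of CCM-3 in unipolar patients. The number of patients affected cannot be estimated from the documents. This should be corrected, but it does not threaten the trial's inference.

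**What to change.** 1. Confirm the sign in the source file.
2. If it is ≤, change the example to a reduction below 50% and PHQ-9 >9. No exception for low first scores is needed: from a first score of 9 or less, this rule prompts only on a rise to 10 or more.
3. In the same sentence, state whether the reduction is measured from the first study score or the previous monthly score.
4. Check that the care-manager manual, training material and audit tool use the corrected rule.

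The cost is one protocol sentence and a check of those materials. The correction stops prompts for patients at 9 or below with a drop under 50%, such as 14 to 9.

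One option is for the investigators to decide: joining the two conditions with *or* would also prompt for patients who halve their score but stay at 10 or more, such as 24 to 12. It would still prompt for 14 to 9, would need an exception for first scores of 9 or less, and would bring somewhat more provider contacts.

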**Table 5: Primary and Secondary Outcomes and Measures – Baseline and Follow-ups**

Aims	Key Measures	Source
Aim 1. Primary outcomes	Mood symptoms: PHQ-9	Patient survey
	Health-related quality of life-SF-12	Patient survey
Aim 1. Secondary outcomes	Guideline concordant care- key measures	Medical record (eTUMS)/claims
	Mood tx: % receiving guideline-concordant antidepressants (if unipolar depression) or guideline-concordant anti-manic treatment (bipolar disorder dx) in 6-month period	Medical record (eTUMS)/claims
	Cardiometabolic monitoring: % receiving lipid profile, fasting glucose or HbA1C	Medical record (eTUMS)/claims
	Hospitalizations (ACSC)	Aetna claims data
	Productivity (Work Limitation Questionnaire)	Patient survey
Aim 2	Organizational data: Practice demographics	Aetna data
	Patient: demographics, comorbidities	Patient survey
Aim 3:	CCM costs, patient inpatient, outpatient, ER, Rx use	Aetna claims, provider survey
	Patient utilities (SF-6)	Patient survey

**The research associate will be blind to random assignment at baseline.** In follow-ups, given the nature of the CCM intervention (CCM-2), there is the possibility that enrolled patients may inadvertently disclose their randomization status with the RA. In pilot studies we found that this is a rare occurrence, but will be mitigated through RA training (e.g., minimizing leading questions that would disclose treatment assignment).

**Primary Aim 1 (patient-level quality of life, symptoms)** include changes in mood symptoms based on the PHQ-9 (102, 103) or ISS (52, 104-106) and health quality of life via the SF-12 Mental and Physical Health Component Scores (**MCS/PCS**; 85,113).

**Patient-level secondary outcomes** include guideline-concordant (quality of) care, hospitalizations, as well as self-reported productivity. These measures are based on recommended indicators from the Accountable Care Organization published rules for performance measures and shared savings (111). We will apply previously established quality measures for mood disorders (98, 111, 112), and cardiometabolic management (113, 114) (Table 5). Quality of care data will be gathered from electronic medical records (eTUMS) and **hospitalization data** will be ascertained from Aetna utilization and claims files at the end of patients' 12 and 24-month participation in two prospectively observed 6-month intervals. Preventable hospitalizations over the 12 and 24-month period will be defined using the AHRQ Ambulatory Care Sensitive Condition (ACSC) definition (115), which identifies conditions for which "good" outpatient care can potentially prevent the need for hospitalization or for which early intervention can prevent complications or more severe disease. We will also assess the probability of psychiatric rehospitalization separately. **Patient-level productivity** over the 24-month period will be assessed in the survey using the Work Limitation Questionnaire(116).

**Patient factors** include CCM engagement ascertained from the patient survey. Engagement is based on the six-item Preference Index for Decision-Making (**API-D**; (117, 118)) which has been used in chronically ill samples to investigate the desire for collaborative care from clinicians. Other patient factors include demographic and clinical information, including co-occurring symptoms (substance use (121, 122), comorbidities (from eTUMS).

**Aim 3: Utilization, costs, CEA, and business case:** Primary utilization measures of interest, including outpatient services, inpatient (including length of stay), and ER use, and health care costs will be ascertained from Aetna eTUMS electronic record reviews using a standard assessment tool (125). Cost data will be estimated for each inpatient, ER, and outpatient visit using Current Procedural Terminology (CPT) codes. A relative value unit (RVU) weight will allow for the use of the Medicare Fee Schedule to calculate a standardized cost for each service. Costs incurred in different years will be discounted at an annual rate of 3% and adjusted for inflation and discounted to the baseline (first) year of the study. Other costs incurred by the participants including medications, visit co-pays, transportation, and time involved in the CCM will be ascertained from the

patient survey. CCM cost data will be estimated using a time-motion survey developed by study investigators (R01 MH 79994) administered monthly to the CMs and quarterly to providers over a 2-year period, which ascertains time spent on CCM activities, including self-management, phone contacts, and documentation.

**C.5.g. Analyses.** General approach: The principal analyses will be for the primary hypotheses. An intent-to-treat analysis will be performed for all analyses. Bivariate baseline analyses will first be conducted to see if randomization was successful by comparing patient demographics and clinical characteristics (e.g., mental health diagnoses) between randomization groups. If there is a lack of equal distribution across groups, these variables will be added as covariates to analyses or propensity scoring will be used. Baseline characteristics will be compared among those enrolled but dropped out over time to those who remained in the study. Our unit of analysis for patient-level outcomes will be patients nested within practices with an indicator for non-solo practice provider sites (126, 127) and an indicator for patients diagnosis (bipolar vs. unipolar depression).

Missing Data: We attained subject retention of 80% over a three-year follow-up in one study (50, 51), and recent 1-year data (MH0745409) indicate 90% retention. Extent and pattern of missingness will be examined for outcome variables as well as for baseline covariates. We expect missingness to be completely at random or at random, in which case the proposed analytical methods will give unbiased estimates of treatment comparison. We will examine how sensitive our conclusions are to potential non-ignorable missingness using a pattern mixture model that will allow us to either model the observed pattern of missingness or change the imputations to represent the likely differences in conditional distributions between observed and missing data (128, 129). For the latter, we will combine the results from each imputed data using Rubin's rules (130).

**Aim 1 primary outcomes (H1a: symptoms, quality of life):** Primary outcomes are continuous, and based on pilot data, are expected to be normally distributed. If a continuous outcome exhibits a significant lack of normality, other options will be considered including data transformation, categorization, and non-parametric analyses. Four linear mixed-effects models accounting for clustering will be run to assess the CCM effects compared to EC on changes in PHQ-9, ISS, and SF-12 PCS and MCS scores over 12-months, adding baseline values of the outcome measure, the effect of CCM, time, and CCM X time interaction.

**Aim 1 secondary analyses:** For guideline concordance and hospitalization, we will compare the likelihood of receiving the guideline-concordant treatment over 12 months (Table 5) as well as the likelihood of an ambulatory care sensitive admission using a generalized linear mixed-effects model (GLM) with logit link. Similar to our primary hypotheses, linear mixed-effects models will be conducted to determine the effect of CCM vs. EC on changes in the Work and Social Adjustment Scale.

**Aim 2 analyses are considered exploratory** but will be used to gain insight into the mechanisms by which CCM impacts patient outcomes. We will first explore the strength and direction of the association between patient-level CCM engagement (API-D scores- see section C.5.f) (119) on changes in outcomes (SF-12, PHQ-9 and ISS scores) by adding patient-level API-D scores to the aforementioned linear mixed-effects models from Aim 1. We will also be run exploratory analyses in which we add key organizational factors (e.g., non-solo practice, practice type-primary care vs. behavioral health, presence of non-MD clinical staff, EMR use, ownership), and other patient factors (e.g., demographics, comorbidities) in the models specified in Aim 1. In secondary analyses we will also incorporate the number of additional optional sessions covering supplemental modules completed by the patient (Section C.5.d).

**Aim 3: Both a payer and societal-based cost-effectiveness analysis (CEA) will be conducted.** A CEA from the payer perspective will involve comparison of utilization costs of health service providers including CM's time ascertained from time-motion survey. A societal perspective will add non-health care costs incurred by patients including time and transportation. Generalized Linear Models with log link functions will be used to correct for heteroscedasticity and reduce the impact of outliers (131). The incremental effectiveness of CCM compared to EC will be measured by changes in health utilities, assessed using a method described by Zivin (132) and Brazier (133) which translates six of the SF-12 items to changes in health utility (SF-6) based on responses to standard gamble questions given by community members regarding all combinations of possible health states. Cost-effectiveness ratios will be calculated based on the difference in per patient costs and effectiveness of CCM versus EC. To quantify uncertainty around these ratios, a standard nonparametric

bootstrapping approach will be employed. For the business case, additional analyses will be conducted in which changes over time in utilization and costs of inpatient, ER, and outpatient services (medical, psychiatric) will be compared between patients in the CCM or EC arms over a 2-year period, in order to determine the time dynamics by which the CCM led to changes in health care costs. Additional cost analyses will take into consideration the return-on-investment of the CCM and changes in enrollee turnover (134).

**C.5.h. Business plan development (Aim 3).** The business case development plan is based on our Enhanced REP framework (73) and informed by the work by Leatherman and colleagues (also see Appendix for submitted paper on business case). In brief, a business case for the CCM exists if the Aetna realizes a financial return on investment or other positive impact on organizational function or sustainability within a “reasonable” time frame (134). Other positive impacts beyond the potential cost savings from implementing CCM include revenue-based from the payer perspective (i.e., value added to payers when the health plan offers CCMs in terms of improved enrollee health and access to care). We chose 2 years as the time frame for outcomes in this study because prior research on CCMs has not found a return-on-investment within one year (3), and 2 years is below the average tenure of an Aetna enrollee. From a business case standpoint, attrition from the health plan may attenuate savings from the initial investment, and our analysis will implicitly account for this by only counting within-plan utilization costs. Enhanced REP addresses organizational and financial incentives (Table 6) designed to inform the CCM return-on-investment (73) and will lead to the development of a reimbursement model for CCMs. Preliminary stages for business case development (134), including (a) the implementation of a program (CCM) shown to improve patient health (135), (b) establishment of quality and cost indicators aligned with existing national initiatives (e.g., ACOs), and (c) identification of a health plan champion and consultant team have been completed. The remaining years (3-5) will be devoted to refining and marketing the business plan, which will include a CCM reimbursement strategy.

